8.4.8 REPORTING OF PREGNANCY

All initial reports of pregnancy in female participants or partners of male participants must be reported to the sponsor by the study-site personnel within twenty-four (24) hours of their knowledge of the event using the appropriate pregnancy notification form. Abnormal pregnancy outcomes (e.g. spontaneous abortion, fetal death, stillbirth, congenital anomalies, ectopic pregnancy) are considered SAEs and must be reported on the SAE page of the eCRF. Participants who become pregnant should permanently discontinue treatment with rNAPc2. Management of heparin-allocated participants should be deferred to the participant's treating physician for thrombotic risk assessment.

Follow-up information regarding the outcome of the pregnancy and any postnatal sequelae in the infant will be required.

9 STATISTICAL CONSIDERATIONS

9.1 STATISTICAL HYPOTHESES

During Phase 2b, the null hypothesis for the primary endpoint is that treatment with rNAPc2 and heparin will similarly reduce D-dimer at Day 8; the alternative hypothesis is that rNAPc2 is superior to heparin in reducing D-dimer.

During Phase 3, the null hypothesis for the primary endpoint is that time to recovery within 30 days of randomization is similar for treatment with rNAPc2 and heparin; the alternative hypothesis is that rNAPc2 is superior to heparin by promoting shorter time to recovery.

9.2 SAMPLE SIZE DETERMINATION

During Phase 2b, approximately 160 participants will be enrolled and randomized 1:1:2 to rNAPc2 dose regimen 1, rNAPc2 dose regimen 2, and heparin standard of care, respectively. Assuming approximately 20% of participants may not be evaluable for any reason, 160 randomized participants will provide for approximately 130 evaluable participants. At a sample size of 160 or greater, the study will have adequate power across a range of effect sizes. This sample size was selected to ensure inferences for the primary endpoint analysis will be robust, given certain potential confounding factors such as missing data (random or non-random), heterogeneous application of heparin (low molecular weight and unfractionated; prophylactic and therapeutic), effects of subject-level covariates (e.g., comorbidities), and effects of site-level covariates (e.g., country).

		Power, Primary Endpoint					
		Effect Size (Proportional Reduction)					
		Enrolled Subjects	Evaluable Subjects	20%	25%	30%	35%
Sample Size	80	64	55.8%	67.4%	75.6%	81.0%	84.5%
	100	80	60.5%	72.7%	80.1%	84.9%	87.8%
	110	88	63.6%	76.2%	80.7%	86.6%	89.2%
	120	96	65.2%	78.0%	82.8%	86.9%	91.0%
	130	104	68.2%	79.3%	84.8%	88.7%	91.7%
	140	112	68.9%	80.7%	86.6%	89.3%	92.5%
	160	128	71.3%	83.1%	88.3%	91.3%	94.1%
	180	144	74.9%	84.5%	89.5%	92.5%	94.6%
	200	160	77.2%	86.5%	91.0%	93.8%	95.8%
*Significance via $\alpha = 0.05$							
†Simulated with 20% Missing Data							
‡Percentages as Averages Across Other Simulation Conditions							

During Phase 3, 450 patients yielding 360 recovery events randomized 1:1 into the two treatment groups have approximately 80% power with 5%, two-sided type 1 error assuming median recovery times of 11 and 15 days for the rNAPc2 and heparin groups, respectively (i.e., treatment hazard ratio (HR)=1.36). As described in [Section 9.4.6 Planned Interim Analyses](#), at the second Phase 3 interim analysis (67% of the initial target number of events), if conditional power, based on the estimated interim hazard ratio, falls within 30% and 80%, the sample size and target number of events will be increased to target 90% conditional power for the final analysis.

9.3 POPULATIONS FOR ANALYSES

Randomized participants consist of all screened participants with randomization assignment, regardless of whether or not study intervention was administered. Participants treated without being randomized or treated before randomization will not be considered as randomized and will not be included in any analysis population. The safety experience of these participants will be reported separately, and they will not be included in the safety population.

The efficacy analysis population will be the intent-to-treat (ITT) population, consisting of all randomized participants as defined above. Participants in the ITT population will be analyzed according to the treatment group allocated by randomization.

An additional efficacy analysis population for sensitivity analyses of the primary efficacy endpoints will be the modified intent-to-treat (mITT) population, consisting of the subset of the ITT population that received at least one dose of study drug. Participants in the mITT population will be analyzed according to the treatment group allocated by randomization.

A per protocol population will include all participants who are randomized and receive all three doses of study drug post-randomization. Participants will be analyzed according to the treatment actually received.

The safety analysis population will be the safety population, consisting of the randomized population who received at least one dose or part of a dose of study treatment. Participants will be analyzed according to the treatment received (rNAPc2 or heparin).

9.4 STATISTICAL ANALYSES

9.4.1 GENERAL APPROACH

The statistical analyses described in this section will be performed as further detailed in a separate statistical analysis plan. The statistical analysis plan will supersede the protocol in the event of any differences between the two documents in the plans for data analysis, and the protocol will be amended if appropriate. The statistical analysis plan will be included as an appendix in the clinical study report for this protocol.

Descriptive statistics for continuous variables will include the number of participants, mean and standard deviation, median, first and third quartiles, and minimum and maximum values. Descriptive statistics for categorical variables will contain count and percentage.

9.4.2 ANALYSIS OF THE PRIMARY EFFICACY ENDPOINT(S)

Phase 2b: Primary efficacy endpoint is change in D-dimer level from Baseline to Day 8, or day of discharge if prior to Day 8. The change in D-dimer will be calculated using proportional change in D-dimer level from the level at baseline to the level at either Day 8 or discharge if discharge occurs before Day 8. A Wilcoxon rank sum test will be performed to compare baseline and Day 8 (or early discharge) D-dimer levels within each treatment group. A second Wilcoxon rank sum test will be used to compare proportional change from baseline to Day 8 (or early discharge) between treatment groups. The primary analysis will involve a comparison of the pooled rNAPc2 treatment groups against the heparin treatment group. Secondary and sensitivity analyses of the primary endpoint will be conducted as described in the statistical analysis plan.

Because the optimal dose rNAPc2 is unknown and its determination is a key objective of the Phase 2b study, the assumption that both doses will be effective and thus can be pooled for statistical analysis may not be correct. Therefore, a series of secondary analyses will be conducted, consisting of analysis for dose response, effectiveness in a single dose group, effectiveness that is related to the extent of baseline D-dimer elevation, and the subgroup analyses described in [Section 9.4.7 SubGroup Analyses](#).

Missingness within the data is to be expected. Subject profile, mortality, or early discharge give rise to the possibility that nonrandom attrition may bias the point estimate for the treatment effect for the primary endpoint. Therefore, missingness will be handled by multiple imputation during a sensitivity analysis as described in the Statistical Analysis Plan (SAP).

Phase 3: The primary efficacy endpoint is time to recovery by Day 30, with day 1 being the date of randomization. Recovery is defined as the first day a participant meets criteria for category 6, 7 or 8 of the ACTT ordinal scale. The analysis of the primary efficacy endpoint will be a comparison of the two treatment groups by a stratified log-rank test, where stratification is according to local laboratory screening D-dimer level $>$ or $\leq 2X$ local laboratory ULN. Cumulative incidence by treatment group will be

summarized by Kaplan-Meier estimates. Additionally, a treatment hazard ratio and corresponding 95% confidence interval will be estimated by a Cox proportional hazard model stratified by local laboratory D-dimer level at screening.

In the analysis of the primary efficacy endpoint, participants who die within 30 days of randomization will be censored at Day 30. In addition, participants surviving to Day 30 who have not met the criteria for recovery by the time of their last ACTT scale assessment on or prior to Day 30 will be censored on the day of their last assessment. There will be no censoring prior to Day 30 due to study treatment discontinuation, initiation of non-study treatment, or intermittently missed ACTT scale assessments.

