In addition to the unblinded interim analyses described above, given that the Phase 3 is event-driven and participants are followed for the primary endpoint for a fixed period of time (30 days), the event rate will be monitored in a blinded fashion throughout the study. If the blinded (noncomparative) event rate indicates that less than 360 primary events are unlikely to be observed among 450 randomized participants – or the upsized number of events and participants based on the conditional power analysis

at the second interim analysis described above – the number of randomized participants will be increased to ensure the target number of events is achieved.

The alpha level for the final analysis will be 0.05 – 0.0001, or 0.0499.

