9.4.7 SUBGROUP ANALYSES

For the primary efficacy endpoint for each Phase, the treatment effects across the following subgroup factors will be examined:

- D-dimer
- Gender
- Age group (<65, ≥65 years)
- Race/ethnicity
- Planned or ongoing therapy with an agent with demonstrated efficacy in patients with COVID-19 (yes, no)
- Baseline ACTT ordinal scale category
- Background antiplatelet therapy at baseline

For the Phase 2b primary efficacy endpoint, possible heterogeneity in the treatment effect for subgroups within each factor will be assessed by including the factor and the interaction between the factor and treatment in the analysis of covariance (ANCOVA) model.

Additionally, the heterogeneous application of heparin dichotomized by therapeutic vs. prophylactic uses, as well as the different standards of use across site, pose the need for sensitivity analyses to determine the degree to which the primary endpoint finding generalizes across sites.

Similarly, for the Phase 3 primary efficacy endpoint, possible heterogeneity in the treatment effect for subgroups within each factor will be assessed by including the factor and the interaction between the factor and treatment in the Cox proportional hazards model.

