7.2.2 Time to Recovery

Time to recovery by Day 30, with Day 1 being the date of randomization. Recovery is defined as the first day a participant meets criteria for category 6, 7, or 8 of the ACTT ordinal scale. The analysis of time to recovery will be a comparison of the combined rNAPc2 dose groups vs. SoC heparin by a stratified log-rank test, where stratification is according to local laboratory screening D-dimer level \leq or $> 2 \times$ local laboratory ULN. Cumulative incidence by treatment group will be summarized by Kaplan-Meier estimates. Additionally, a treatment hazard ratio and corresponding 95% confidence interval will be estimated by a Cox proportional hazard model stratified by local laboratory D-dimer level at screening. In addition, the two rNAPc2 dose groups will be compared for time to recovery.

Participants who die within 30 days of randomization will be censored at the day $x+1$, where x denotes the longest observation window among all subjects in the analysis. In addition, participants surviving to their Day 30 visit who have not met the criteria for recovery by the time of their last ACTT scale assessment on or prior to the Day 30 visit will be censored on the day of their last assessment on or prior to the Day 30 visit. There will be no censoring prior to Day 30 due to study treatment discontinuation,

initiation of non-study treatment, or intermittently missed ACTT scale assessments. Patients lost to follow-up or otherwise of unknown status occurring prior to Day 30 will be censored based on, and at the day of, the last known status.

The frequency and percentage of participants with each recovery category (ACTT equal to 6, 7, or 8) will be summarized.

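### Cheap improvement: the Phase 3 time-to-recovery test stratifies on screening D-dimer only; adding baseline ACTT category would gain power at little cost

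*Protocol*

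**What the plan says.** **Endpoint and test.** Under Protocol 9.4.2, Phase 3 recovery is the first day in ACTT category 6, 7 or 8, counted to Day 30. "The analysis of the primary efficacy endpoint will be a comparison of the two treatment groups by a stratified log-rank test"; the strata are screening D-dimer above, or at or below, twice the local upper limit of normal. The hazard ratio is "estimated by a Cox proportional hazard model stratified by local laboratory D-dimer level at screening". This matches the randomization stratum (Protocol 4.1, 4.2, 6.3).

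**Baseline ACTT.** It is a baseline characteristic in Protocol 9.4.5. In 9.4.7 "Baseline ACTT ordinal scale category" is a subgroup factor, entered in the Phase 3 Cox model with a treatment interaction. It is not part of the primary test, and no reason is given.

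**Sample size.** Protocol 9.2 plans for "450 patients yielding 360 recovery events randomized 1:1 into the two treatment groups". The power it claims is about 80% at the two-sided 5% level. The effect size comes from "assuming median recovery times of 11 and 15 days for the rNAPc2 and heparin groups, respectively", which it equates to a hazard ratio of 1.36. It gives no mix of baseline categories and no recovery rate by category. It does not say whether 1.36 applies within categories or to the population as a whole. In 9.4.6, "The alpha level for the final analysis will be" 0.0499.

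**Phase 2b.** SAP 7.2.2 uses the same form: a "comparison of the combined rNAPc2 dose groups vs. SoC heparin by a stratified log-rank test", again with D-dimer strata only.

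**Timing of ACTT.** The Baseline visit in Protocol 8.1.3 lists no ACTT assessment. The first one listed is at Day 2, 24 hours after the first dose.

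**The concern.** Protocol 8.2 places hospitalized patients in categories 2 (invasive ventilation or ECMO) to 5 (no supplemental oxygen). Eligibility sets no oxygen or ventilation limit (Protocol 5.1, 5.2), so the starting mix could be wide. A patient in category 5 is one step from recovery; a patient in category 2 is four steps away.

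In a log-rank or Cox analysis, leaving out a strong prognostic factor pulls the estimated hazard ratio towards 1, even when the arms are balanced on that factor. Stratifying on it compares like with like and also removes chance imbalance in baseline severity. What is at stake is the efficiency of the Phase 3 primary test, not its validity.

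**Working it through.** **1. The plan's own figure.** Schoenfeld power is Φ(½·√events·ln HR − z). With 360 events, ½·√360 = 9.487.
- HR 1.36: 9.487 × 0.3075 − 1.960 = 0.957, power 83.1% (83.0% at alpha 0.0499).
- HR 15/11: 9.487 × 0.3102 − 1.960 = 0.982, power 83.7%.
- Expected events, exponential recovery over 30 days: 225 × (1 − 2^(−30/11)) + 225 × (1 − 2^(−30/15)) = 225 × (0.849 + 0.750) = 359.8. The 360 events reproduce.
- If the non-binding 10% conditional-power futility rule is obeyed: 81.4–82.1%.

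The stated 80% is therefore about 3 points conservative.

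**2. Margin before 80% is lost.** At 360 events, 80% power needs ln HR = (1.961 + 0.842)/9.487 = 0.2954, so HR = 1.344. Against ln(15/11) = 0.3102 that is a shrinkage of about 5%.

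**3. Effect of leaving ACTT out (simulation).** N = 450, 1:1, exponential recovery within category, daily times, 30-day follow-up, alpha 0.0499. The control median is set to 15 days and the hazard ratio to 15/11 within each category. The treated curve is then the control curve with time divided by 15/11, so the overall medians remain 15 and 11 days. Three inputs are assumptions: the category mix, the factor by which the recovery rate falls per category, and the reading of 15/11 as a within-category effect. Results from 4,000 trials per setting, rounded to whole percent, so differences may be off by a point:

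| Mix in ACTT 5/4/3/2 | Factor | D-dimer only | ACTT only | D-dimer × ACTT |
|---|---|---|---|---|
| 15/45/25/15% | 1.0 | 83 | 83 | 82 |
| | 1.25 | 81 | 82 | 81 |
| | 1.5 | 76 | 82 | 82 |
| | 2.0 | 65 | 82 | 81 |
| 20/60/15/5% | 1.5 | 79–80 | 83 | 82–83 |
| | 2.0 | 72 | 81–82 | 80–81 |

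With ACTT pooled as 5 / 4 / 2–3 (3,000 trials), power for D-dimer only versus D-dimer × ACTT was:
- First mix: 82.4 vs 83.5 (factor 1.25), 77.5 vs 82.0 (1.5), 65.0 vs 78.2 (2.0).
- Second mix: 82.7 vs 82.7, 78.9 vs 81.9, 72.5 vs 80.6.

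Pooling keeps most of the gain: about 8 and 13 points at factor 2.0.

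**4. A second set of assumptions.** Recovery rates for categories 2/3/4/5 relative to category 4, with mix 10/20/50/20% (15/25/40/20% in the strong case). Power for D-dimer only → D-dimer + ACTT:

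| Rate ratios | N = 450 | N raised to give 360 events |
|---|---|---|
| Weak 0.7/0.85/1/1.15 | 82.8 → 83.0 | 82.4 → 82.6 |
| Mild 0.5/0.7/1/1.3 | 79.5 → 82.7 | 79.5 → 82.2 |
| Moderate 0.3/0.5/1/1.5 | 73.0 → 81.1 | 74.8 → 83.3 |
| Strong 0.15/0.35/1/2 | 55.2 → 78.8 | 59.2 → 82.4 |

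With no treatment effect, the D-dimer-only test rejected in 2.3–2.7% one-sided. Type I error is intact.

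**The case against.** **The shortfall is not in the documents.** This stands. If 1.36 is the effect that the planned D-dimer-stratified test would see, power is about 83% and nothing falls below 80%. The protocol does not say which reading is meant. The gain from stratifying survives either reading: if the population-level effect is roughly as planned, the within-category effect must be larger. At within-category HR 1.42 (factor 1.5) power goes from 87% to 91%; at 1.50 (factor 2.0), from 86% to 95%.

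**The adaptive rules protect power.** This stands in part. Phase 3 is event-driven (Protocol 7.2), blinded monitoring adds participants until the event target is reached, and the promising zone can raise the target to 480 events (9.4.6). With N raised to give 360 events and the promising zone applied, the D-dimer-only test has about 84–86% power at factor 1.25, 81% and 84% at 1.5 (79% and 82% if futility is always obeyed), and 71% and 79% at 2.0. Restoring the event count does not undo a diluted hazard ratio, and the promising zone may use up to 150 more participants. An ACTT-stratified test would benefit from the same rules.

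**A factor of 2.0 is large.** It means a 2 × 2 × 2 = 8-fold rate difference between categories 5 and 2. Nothing in the documents supports or excludes that.

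**The choice is conventional, and a Phase 3 SAP may change it.** Analysing by the randomization stratum is standard, and Protocol 4.2 explains the choice of D-dimer. SAP section 1 says Phase 3 reporting will have its own plan, and under Protocol 9.4.1 a SAP supersedes the protocol. That plan is not available here and might add ACTT. The protocol text as it stands does not.

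**Phase 2b.** SAP 7.2.2 carries no power claim, and secondary endpoints there also receive subgroup models that include baseline severity (SAP 5.3, 11.2, 11.3, 14.1). The point has little force for that analysis.

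**Conclusion.** The Phase 3 primary test and Cox model leave out baseline ACTT and give up power to the extent that it is prognostic. At fixed N = 450 and within-category HR 15/11, the gain from adding it is about 0–2 points at a 1.25-fold fall in recovery rate per category, 2–5 at 1.5-fold and 9–17 at 2-fold. The cost is about 1 point if ACTT is not prognostic. All of this rests on assumed mixes and rate ratios.

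A reader might infer that Phase 3 misses its stated 80% power. The documents do not support that: their inputs give about 83%. A fall below 80% requires both that 1.36 is a within-category effect and that ACTT is strongly prognostic (about 1.5-fold per category or more at fixed N), and the adaptive rules then offset part of it. Nor should a reader infer that the test is invalid, or that the plan overlooks baseline ACTT; it is absent from the primary analysis only. This is an inexpensive efficiency improvement.

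**What to change.** 1. In Protocol 9.4.2 (Phase 3) and the separate Phase 3 SAP, stratify the log-rank test and Cox model by D-dimer stratum and baseline ACTT category, pooled by a rule fixed in advance, for example 5 / 4 / 2–3. Alternatively, keep the D-dimer strata and add baseline ACTT as a pre-specified Cox covariate, naming its treatment test as primary.
2. Add a pre-dose Day 1 ACTT recording to the Baseline visit (Protocol 8.1.1 and 8.1.3). A Day 2 score is post-dose and must not serve as a stratum. Protocol 9.4.5 and 9.4.7 need the baseline value in any case.
3. In Protocol 9.2, state whether HR 1.36 is a within-stratum or a population-level effect.
4. Optionally, make the same change in SAP 7.2.2 for consistency.

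Cost: wording changes, one extra baseline item, some small strata, and about 1 point of power or less if ACTT is not prognostic. No additional participants are needed.

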9.4.3 ANALYSIS OF THE SECONDARY ENDPOINT(S)

Phase 2b: Proportional change in D-dimer level from Baseline to 24 hours post-dose (Day 2) and Day 3 and change in the additional biomarkers associated with outcomes, including those related to coagulation and inflammation from baseline through Day 8, will be analyzed by the same methods as described for the primary efficacy endpoint. Time-to-event outcomes will be analyzed by the same methods as described for Phase 3.

Phase 3: Time to first occurrence of a composite of thrombotic events and all-cause mortality within 30 days of randomization and time to all-cause mortality within 30 days of randomization will be analyzed by the same methods as described for the primary efficacy endpoint, with the exception that deaths will be counted as an event. Events included in these analyses will be those as adjudicated by the CEC. Participants without an adjudicated event by Day 30 will be censored on the study day of last contact or Day 30, whichever is earlier. Similar to the primary endpoint, there will be no censoring prior to Day 30 due to study treatment discontinuation or initiation of non-study treatment. The analysis method for the proportion of participants alive and out of the hospital at 30 days post-randomization will be specified in the Statistical Analysis Plan (SAP) which will also include a multiplicity plan for alpha allocation within the secondary endpoints.

Change in the biomarkers associated with outcomes including those related to coagulation and inflammation will be analyzed by the same methods as described for Phase 2b.

Days in intensive care unit, on ventilator, vasopressors, renal replacement therapy, and circulatory support will be summarized with descriptive statistics.

9.4.4 SAFETY ANALYSES

Incidence rates of AEs including adjudicated bleeding events, all, serious, fatal, severe and treatment-related AEs reported throughout the conduct of the study will be tabulated by preferred term and system organ class.

Changes in laboratory values and vital signs will be summarized with descriptive statistics. The incidence of concomitant medications will also be summarized.

Drop in hemoglobin level as reported per local laboratory data will be used as an indicator of potential bleeding risk.

9.4.5 BASELINE DESCRIPTIVE STATISTICS

Baseline demographic information and patient characteristics including, but not limited to, gender, race, age, COVID-19 symptoms, ACTT ordinal scale category, study entry D-dimer median value, remdesivir or other antiviral therapy, concomitant medications, vital signs, and laboratory parameters will be summarized by treatment group for the ITT population.

